6.2 Analysis Population Set(s)

For each treatment per body site, the number of subjects randomized, the number of subjects available for mITT analysis [average treatment effect (ATE), responder rate and product expression volumes] and / or for per-protocol analysis [average treatment effect (ATE), responder rate and product expression volumes] at each post-treatment time point (30 seconds, 10 minutes and 6 hours) will be provided in tables below (cf. Table 2, Table 3 and Table 4). If the number of subjects randomized is different from the number of subjects randomized with treatments received, the number of subjects randomized with treatment received will be also summarized.

Table 2: Number of subjects randomized

Treatment	Body Site	N Subjects Randomized with Treatment Received
A	Abdomen	
B	Abdomen	
C	Abdomen	
D	Abdomen	
A	Groin	
B	Groin	
C	Groin	
D	Groin	

Table 3: Number of subjects available for mITT analysis

Treatment	Body Site	N Subjects for mITT ATE at 30 sec	N Subjects for mITT ATE at 10 min	N Subjects for mITT ATE at 6 hr	N Subjects for mITT Responder Rate at 6 hr	N Subjects for mITT Product Expression Volumes
A	Abdomen					
B	Abdomen					
C	Abdomen					
D	Abdomen					
A	Groin					
B	Groin					
C	Groin					
D	Groin					

Table 4: Number of subjects available for per-protocol analysis

Treatment	Body Site	N Subjects for Per-Protocol ATE at 30 sec	N Subjects for Per-Protocol ATE at 10 min	N Subjects for Per-Protocol ATE at 6 hr	N Subjects for Per-Protocol Responder Rate at 6 hr	N Subjects for Per-Protocol Product Expression Volumes
A	Abdomen					
B	Abdomen					
C	Abdomen					
D	Abdomen					
A	Groin					
B	Groin					
C	Groin					
D	Groin					

7 Statistical Analysis/Calculations

7.1 Derived Variables

7.1.1 Log CFU/cm² of skin

The estimated log₁₀ number of viable microorganisms per cm² recovered from each sample site will be designated the “R-value”. To convert the volumetric measure of the sample into the number of colony-forming units per square centimeter (cm²), the following formula will be employed:

$$R = \log_{10} \left[\frac{F \left(\frac{\sum_{i=1}^2 C_i}{n} \right) 10^{-D}}{A} \right] \quad (1)$$

Where:

R = the average colony-forming unit count in log₁₀ scale per cm² of sampling surface

F = Total number of mL of sampling solution added to the sampling cylinder (in this study, F = 6 mL for all samples)

$\frac{\sum_{i=1}^2 C_i}{n}$ = average of the duplicate colony counts used for each sample collected (n = 2)

D = Dilution factor of the plates counted

A = Inside area of the sampling cylinder (A= 3.46 cm² in this study)

Note: The reason that a log₁₀ transformation will be performed on the collected data is to obtain a linear scale. A linear scale, more appropriately a log₁₀ linear scale, is a basic requirement of the statistical models used in this study.

If colonies on one of the plates are uncountable, the count from the remaining plate will be used.

In order to avoid potential calculation problems due to taking the logarithm of zero, counts of less than 1 CFU/cm² are treated as 1 CFU/cm², such that the log₁₀ transformation is no less than zero.

7.1.2 Log Reduction

Log₁₀ CFU/cm² reductions from baseline will be calculated separately for each subject, each post-application time point, and each of the treated anatomical sites by taking the baseline log₁₀ CFU/cm² values and then subtracting the log₁₀ CFU/cm² values for the samples taken after the baseline.

7.1.3 Responder Rate

Responder statuses for each subject will be evaluated separately for each of the four sites and separately at 6 hours post-application time point based on the log₁₀ CFU/cm² changes from baseline. A subject is considered a responder at the 6-hour sample time for the abdomen or groin if the log₁₀ CFU/cm² reduction is equal to or greater than 0.

7.1.4 Product Expression Volumes

The weight of drug product applied to a test site will be estimated by subtracting the weight measurement of the test material after the application from the weight of the test material before application.

7.2 Handling of Missing Data

For mITT responder rate analysis, subjects with missing data at either baseline or a certain time interval will be included as non-responders for that time interval. Responder rate analysis will be performed based on both

per-protocol data and mITT data if there are any missing data identified and if per-protocol data and mITT data are different.

For average treatment effect (ATE), log reduction and product expression volumes, missing data will not be imputed for mITT data. Analysis will be performed based on the per-protocol data as supportive analyses when per-protocol data are different from mITT data.

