##### Data sets analyzed

The full Intent to Treat (ITT) data set (all randomized subjects) will be used for the safety analysis.

A modified Intent to Treat (mITT) data set will be used for efficacy analyses. Inclusion for the mITT data set is evaluated for each body area (left and right for the inguen and abdomen). For each body area, if the treatment day baseline bacterial count requirements are in the range of 3.00 to 5.50  $\log_{10}/\text{cm}^2$ , inclusive, on the abdomen and 5.00 to 7.50  $\log_{10}/\text{cm}^2$ , inclusive, on the inguen, then the data are included in the mITT data set. Data collected will be excluded from Per Protocol data if the treatment-day baseline counts are outside the acceptable range. Analyses conducted on the mITT data set will also be conducted on the Per Protocol data set as supportive analyses when Per Protocol data are different from mITT data.

- For  $\log_{10}$  CFU/ $\text{cm}^2$  determinations, missing data will not be imputed for either mITT data or Per Protocol data and will be excluded from analysis.
- For responder rate calculations from 6-hour data, missing data will be treated as non-responders in the mITT data, while in the Per Protocol data, missing data will not be imputed and will be excluded from the responder rate Per Protocol analysis.

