6.1 Data Sets Analyzed

Descriptions of the modified intent to treat (mITT) data, per-protocol data and intent to treat (ITT) data are shown below. Inclusion for the per-protocol data / mITT data set is evaluated for each body area (left and right for the groin and abdomen).

- Modified Intent to Treat (mITT) data: data collected will be included if the treatment-day baseline counts are within the acceptable range ($\geq 3.00 - \leq 5.50 \log_{10} \text{CFU/cm}^2$ on abdominal area, and $\geq 5.00 - \leq 7.50 \log_{10} \text{CFU/cm}^2$ on inguinal area). Data collected will be excluded from mITT data if the treatment-day baseline counts are outside the acceptable range.
 - For responder rate at 6 hours post-treatment time point, missing data at either baseline or a certain time interval will be imputed as non-responders for that time interval in the mITT data.
 - For average treatment effect (ATE) and \log_{10} reduction, missing data will not be imputed for mITT data.
- Per-Protocol data: data collected will be included if the treatment-day baseline counts are within the acceptable range ($\geq 3.00 - \leq 5.50 \log_{10} \text{CFU/cm}^2$ on abdominal area, and $\geq 5.00 - \leq 7.50 \log_{10} \text{CFU/cm}^2$ on inguinal area). Data collected will be excluded from per-protocol data if the treatment-day baseline counts are outside the acceptable range.
 - Missing data at any time interval will not be imputed for ATE, responder rate and log reduction. Missing data will be excluded from per-protocol ATE, responder rate and log reduction analysis.
- Intent to Treat (ITT) data: all randomized subjects with available data will be included and used for the ITT analysis. The full intent to treat (ITT) data set (all randomized subjects) will be used for the safety analysis.

For ATE, responder rate and log reduction, efficacy analyses will be first made on the modified intent to treat (mITT) data set. Efficacy analyses will be also conducted on the per-protocol data set as supportive analyses when per-protocol data are different from mITT data.

For product expression volumes, inclusion of data points will be based on whether the matching data point is included for efficacy for ATE. Analysis will be performed based on the per-protocol data as supportive analyses when per-protocol data are different from mITT data for product expression volumes.

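### SAP 6.1 and 7.2 score a site with no baseline count as an mITT non-responder at 6 hours, although mITT membership is defined by an in-range baseline

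*SAP*

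**What the plan says.** **Who is in mITT.** SAP 6.1 works by site: "Inclusion for the per-protocol data / mITT data set is evaluated for each body area" (left and right, groin and abdomen). For mITT, "data collected will be included if the treatment-day baseline counts are within the acceptable range", which is 3.00 to 5.50 log10 CFU/cm² on the abdomen and 5.00 to 7.50 on the groin. The converse sentence reads "Data collected will be excluded from mITT data if the treatment-day baseline counts are outside the acceptable range". Neither sentence mentions a missing baseline. Protocol 15.0 (Data sets analyzed) uses the same ranges as an if-then condition: if the baseline is in range, "then the data are included in the mITT data set".

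**What happens to missing data.** For the 6-hour responder rate, a sub-bullet of the mITT definition in SAP 6.1 says "missing data at either baseline or a certain time interval will be imputed as non-responders for that time interval in the mITT data". SAP 7.2 repeats this: "subjects with missing data at either baseline or a certain time interval will be included as non-responders for that time interval". Protocol 15.0 says of the 6-hour responder calculation that "missing data will be treated as non-responders in the mITT data, while in the Per Protocol data" missing values are left out. It does not mention a missing baseline.

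**What a responder is.** SAP 7.1.3 defines response at 6 hours as a log10 reduction from baseline of zero or more, so the status cannot be worked out without a baseline value.

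**The concern.** The in-range baseline is what qualifies a site for mITT. A site with no baseline count has not been shown to qualify, and its response cannot be determined. Even so, the missing-data rule places it in the responder denominator as a failure. A site whose baseline was observed and fell outside the range is removed and costs the arm nothing.

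The baseline sample is taken before product is applied (Protocol 13.6), so its loss carries no information about persistence. Counting it as non-response pulls that arm's 6-hour rate and lower bound down for a reason unrelated to the product. Because the text neither admits nor excludes such a site in the membership sentences, two programmers could build different 6-hour data sets and each cite the SAP.

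The estimates are meant to inform the design of later studies (SAP section 4), so the denominator behind them should not be open to two readings.

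**Working it through.** **1. Inputs**
- Sites per arm and anatomical region: 36 evaluable (SAP section 4 and Table 1).
- Interval: exact, one-sided, 95% lower bound (SAP 7.3.2).
- Target: a success proportion of at least 95% (SAP 7.3.2). Protocol 15.2 compares both the rate and its lower bound with 95%.
- Number k of treated sites with a missing baseline: not given in the documents. Assumed range: 1 to 4 per arm and region.

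**2. Formula.** For x responders among n sites, the lower bound L solves P(X ≥ x | n, L) = 0.05, that is, L = the 0.05 quantile of Beta(x, n − x + 1). When x = n this reduces to L = 0.05^(1/n).

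**3. The plan's own figures.** SAP Table 7 (an example table) gives 92.0%, 87.5% and 83.5%. The formula gives:
- 36/36: 0.05^(1/36) = 92.02%
- 35/36: 87.49%
- 34/36: 83.53%

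All three reproduce.

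**4. Add k missing-baseline sites as failures, as SAP 7.2 directs.** The 36 sites with an in-range baseline stay as they are, and n becomes 36 + k.

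| Responders | k = 0: rate (bound) | k = 1: rate (bound) | Change in bound, k = 0 to 1 |
|---|---|---|---|
| 36 | 100% (92.0%) | 36/37 = 97.3% (87.8%) | 4.2 points |
| 35 | 97.2% (87.5%) | 35/37 = 94.6% (83.9%) | 3.6 points |
| 34 | 94.4% (83.5%) | 34/37 = 91.9% (80.4%) | 3.1 points |

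With 36 responders, k = 2 gives 36/38 = 94.7% (84.3%) and k = 4 gives 36/40 = 90.0% (78.6%). The loss per site shrinks as k grows: the second site costs 87.8 − 84.3 = 3.5 points.

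**5. If the missing-baseline site is one of the 36.** Protocol 13.3 provides for additional subjects where a baseline is low and does not mention a missing one, so such a site might not be replaced. The comparison is then 35/35, with bound 0.05^(1/35) = 91.8%, against 35/36, with bound 87.5%. The difference is 4.3 points, much the same size.

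**6. Under the protocol's method.** With the two-sided Score interval of Protocol 15.2, 36/36 to 36/37 moves the lower limit from 90.4% to 86.2%, and 35/36 to 35/37 from 85.8% to 82.3%. The size does not depend on the interval method.

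**7. Can the bound reach 95% at all?** With no failures, 0.05^(1/n) ≥ 0.95 first holds at n = 59. At n = 36 the best possible bound is 92.0%, with or without the disputed rule.

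**The case against.** **It may be a deliberate exception.** The inclusion sentence says *if*, not *only if*, and the exclusion sentence removes only counts outside the range. A missing count is neither. The sub-bullet sits inside the mITT definition and is repeated in 7.2, so it can be read as filling that gap conservatively for one endpoint. This stands as far as it goes. A reader might infer that the two rules cannot both be followed, but that is too strong: an analyst could drop out-of-range sites and add missing-baseline sites to the responder analysis only. The SAP does not say that this is intended, however.

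**The protocol's rule is general.** It treats missing data as non-response without limiting that to the 6-hour sample, and the SAP may only be spelling it out. But the protocol applies the rule within the mITT data, which it has just defined by an in-range baseline. Limiting the rule to 6-hour losses is consistent with that text, although the protocol does not settle the question.

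**Table 3.** A reader might take different N in the ATE and responder-rate columns as an error. It is not: missing values are imputed for one and not for the other, so a missing 6-hour count alone would produce the difference.

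**A lost plate is covered.** Plating is in duplicate, and if one plate is uncountable the other is used (Protocol 13.10, SAP 7.1.1). This stands: the sample or both plates must be lost. It can still happen at a treated site, because plates incubate for 72 hours (Protocol 13.8) and the site is treated before its baseline is known.

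**Per-protocol results already show the effect.** That set has the same baseline range, leaves missing values out, and is analysed whenever it differs from mITT. This is a partial safeguard only, since per-protocol also drops missing 6-hour counts and so does not isolate the baseline rule.

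**Conclusion.** The point holds as a minor one. As written, the SAP scores as product failure a site whose eligibility and response are both unknown, which conflicts with its own inclusion condition unless an unstated exception is assumed. The first such site in an arm lowers the bound by 3.1 to 4.2 points when added to 36 evaluable sites. It can also move the reported rate across the 95% comparison value, from 97.2% to 94.6%.

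These sizes rest on an assumed count of missing baselines. If there are none, nothing changes, and duplicate plating makes them likely to be few.

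A reader might infer that the rule could overturn a success conclusion on the lower bound. The figures do not support that: no bound at 36 sites reaches 95% under either reading. The endpoint is secondary, the study is not powered for efficacy, and the rule works against the arm in which it applies. What changes is the reported rate, its bound and its denominator.

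**What to change.** - In SAP 6.1 and 7.2, delete the reference to baseline (the words *at either baseline or*) and adjust the grammar, so that the rule reads in substance: for the mITT responder rate, a missing 6-hour count at a site with an observed in-range treatment-day baseline is scored as a non-responder.
- State in 6.1 that a site with a missing treatment-day baseline is outside mITT. Write the 7.2 rule in terms of sites, since 7.2 speaks of subjects while inclusion is judged per body area.
- Add sites with a missing baseline to the SAP section 8 listing of those not passing the baseline criteria.
- If the conservative rule is intended, state it in 6.1 as an exception for the responder rate and keep it as a sensitivity analysis beside the result without those sites.

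The cost is SAP wording and, if the sensitivity analysis is kept, one further responder-rate table per body site. No data collection or protocol procedure changes.

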7.3 Analysis Methods

For each body site, when per-protocol data are different from mITT data for average treatment effect (ATE), responder rate, log reduction or product expression volumes, per-protocol analysis and mITT analysis will be performed separately using the same statistical methods. The following analysis methods will be applied to both per-protocol analysis and mITT analysis, both abdomen and groin.

An alpha level of 5% (two-sided) is used for all analyses.

7.3.1 Primary Analysis

The primary purpose of the study is to compare the immediate antimicrobial activity of the Investigational Products to the Negative Control and Active Control according to the methods described in the FDA TFM with the statistical analyses outlined in a deferral letter published January 19, 2017. There are two test criteria that drive the hypotheses.

- Evaluate the average treatment effect (ATE) of the Active Control (AC) compared to each Investigational Product (IP) at 30 seconds and 10 minutes for non-inferiority on both abdomen and groin. ATE of the AC compared to either IP is defined as the contrast of the treatment effect of the IP minus the treatment effect of the AC (IP - AC) in the linear regression. Statistical hypotheses are:
 - Ho: The upper bound 95% confidence interval of the ATE of IP - AC $\geq 0.5 \log_{10}$
 - Ha: The upper bound 95% confidence interval of the ATE of IP - AC $< 0.5 \log_{10}$
- Evaluate the Average Treatment effect (ATE) of each Investigational Product (IP) compared to the Negative Control (NC) at 30 seconds and 10 minutes on both abdomen and inguen anatomical area. ATE of the IP compared to the NC is defined as the contrast of the treatment effect of the NC minus the treatment effect of the IP (NC - IP) in the linear regression. Statistical hypotheses are:
 - Ho: The lower bound 95% confidence interval of the ATE of NC - IP $\leq 1.2 \log_{10}$
 - Ha: The lower bound 95% confidence interval of the ATE of NC - IP $> 1.2 \log_{10}$

Ho is the null hypothesis and Ha is the alternative hypothesis.

A linear regression model for each body site will be used for primary analysis. In the model, the response is the post-treatment \log_{10} bacterial counts and predictors are the treatment effect as a fixed effect and the pre-treatment \log_{10} bacterial counts as a covariate. The interaction between the treatment and pre-treatment \log_{10} bacterial counts will be also explored. If there is no significant interaction detected between treatment and pre-treatment \log_{10} bacterial counts, the interaction term will be removed from the model and the average difference between treatments will be estimated from the linear regression model after correcting for pre-treatment \log_{10} bacterial counts. If there is a significant interaction detected between treatment and pre-treatment \log_{10} bacterial counts, the average difference between treatments will be estimated from the linear regression model at the average of the covariate. Additional factors (e.g., technician and subject demographics) may be also included in the model and the effects will be investigated.

Since the study will declare success when and only when both non-inferiority and superiority are demonstrated for both abdomen and groin, no multiplicity adjustment for multiple primary objectives is required.

An example for results of comparisons above can be found in Tables 5 and 6. All results that do not meet the targets are highlighted.

Table 5: Example: ATE for IP1/IP2 - AC for Groin

Comparison	Time Point	N Pairs	Difference in ATE	Conf Int	Meet Non-inferiority Criteria
IP1 - AC	30 Seconds	36	-0.50	-1.31, 0.30	Yes
IP2 - AC	30 Seconds	36	-0.35	-1.00, 0.31	Yes
IP1 - AC	10 Minutes	36	0.32	-0.52, 1.15	No
IP2 - AC	10 Minutes	36	0.50	-0.39, 1.39	No

Table 6: Example: ATE for NC - IP1/IP2 for Groin

Comparison	Time Point	N Pairs	Difference in ATE	Conf Int	Meet Superiority Criteria
NC - IP1	30 Seconds	36	1.35	1.01, 1.59	No
NC - IP2	30 Seconds	36	1.23	0.90, 1.50	No
NC - IP1	10 Minutes	36	0.4	0.02, 0.82	No
NC - IP2	10 Minutes	36	1.6	1.28, 1.91	Yes

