### **13.3 Randomization**

The randomization scheme for the study will be provided by the Study Sponsor. The test materials will be coded as A, B, C, and D and assigned randomly to the subjects per a computer-generated randomization schedule in blocks of 24 subjects. Subjects will be randomized to test all of the Treatment Groups.

Each subject will receive two different treatments, one on the right side of the body and one on the left. The 6 possible combinations for product application is as follows:

- Treatment A / Treatment B
- Treatment A / Treatment C
- Treatment A / Treatment D
- Treatment B / Treatment C
- Treatment B / Treatment D
- Treatment C / Treatment D

A minimum of 72 evaluable subjects will be required to achieve 36 evaluable test sites for each test material: Investigational Product #1, Investigational Product #2, Active Control, and Negative Control arms for inguinal and abdominal regions (at least 144 total test sites for inguinal and abdominal regions).

Subjects will be randomized to treatment using the following block design:

- The study product assignments will be balanced such that the number of readings per anatomical site matches the calculated requirements.
- The application will be randomized so that each treatment is used on an equal number of left and right sides of the body.
- Each inguinal and abdominal sample site is divided into four areas, and all four of the areas are sampled: one at baseline, one at 30 seconds, one at 10 minutes, and one at 6 hours. Therefore, for any inguen or abdomen site there are 24 possible sampling orders.

The number of subjects required for a completely balanced block design for all factors at once (study products, left/right, and sampling order) is a multiple of 288 (6\*2\*24). The number of intended subjects makes it infeasible to provide a completely balanced block design, so the following priority order will be used for design:

1. Treatment combinations will be applied in balanced blocks
2. Left/right balance will be preserved – each treatment will be applied an equal number of times to each side of the body.
3. Sampling orders will be assigned in blocks of 24 as much as possible. If the final number of subjects is not a multiple of 24 the remaining subjects will be assigned random non-duplicate sample orders from the 24 possible sample orders.

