The blocking will be adjusted based on the final subject numbers to be as balanced as possible with respect to all three factors at once, with priority using the order listed above.

Data from test sites that are not evaluable due to low Treatment Day Baseline counts ( $< 3.00 \log_{10} \text{CFU/cm}^2$  on abdomen, and  $< 5.00 \log_{10} \text{CFU/cm}^2$  on inguen) will not be included in the mITT data set, and sufficient additional subjects will be recruited and randomized to meet the minimum number of evaluable test sites/treatment arm.

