3.3 Study Design

This is a single-center and randomized design where each subject receives two different treatments out of 4 treatments, one on the left side of the body and one on the right side. This means there are 6 possible combinations of treatments (assuming A, B and C are either Investigational Product #1, Investigational Product #2 or Active Control, D is the Negative Control): A & B, A & C, A & D, B & C, B & D, and C & D.

A minimum of 72 evaluable subjects will be required to achieve a total of at least 144 test sites for groin and abdominal regions. To achieve 36 evaluable test sites from Investigational Product 1, Investigational Product 2, Active Control and Negative Control arms for groin and abdominal regions, of the minimum 72 evaluable subjects:

- 12 subjects will receive treatments from both A and B.
- 12 subjects will receive treatments from both A and C.
- 12 subjects will receive treatments from both A and D.
- 12 subjects will receive treatments from both B and C.
- 12 subjects will receive treatments from both B and D.
- 12 subjects will receive treatments from both C and D.

The two investigational products and the active control will be randomly assigned codes of A, B or C. However, due to visual differences between each of the test materials, the products cannot be blinded to all study staff. In order to guard against any bias of the study outcome, technicians who participate in product application or sample collection from subjects during treatment day procedures will not participate in the processing of samples. The technicians processing samples and/or counting the resultant plates will be blinded to the study randomization during the data gathering processes. Plate counts will be reviewed and recorded by separate BSLI staff prior to being entered into a data spreadsheet where product information (unblinding) would occur.

Subjects will be sampled for treatment day baseline microbial populations on randomly assigned sites of the abdominal and inguinal areas on both sides. Subjects will have samples collected at baseline, 30 seconds (± 5 seconds), 10 minutes (± 30 seconds) and at 6 hours (± 30 minutes) post-treatment application on both abdomen and inguinal sites. All sampling times will be calculated from the completion of the dry time of each product following application.

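### The primary regression treats the two sides of each subject as independent and pools one variance over four arms, so the width of the deciding 95% intervals cannot be relied on

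*SAP*

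**What the plan says.** Protocol 13.3 describes a split-body design: "Each subject will receive two different treatments, one on the right side of the body and one on the left". SAP 3.3 repeats it and sets the allocation for each of the six product pairs, for example "12 subjects will receive treatments from both A and B". Sides are balanced: "each treatment will be applied an equal number of times to each side of the body".

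For the primary analysis, SAP 7.3.1 says: "A linear regression model for each body site will be used for primary analysis". The response is the post-treatment log10 count. The predictors are treatment, baseline log10 count and, if significant, their interaction. Protocol 7.1 and 15.1 describe the same model. One optional sentence follows in the SAP: "Additional factors (e.g., technician and subject demographics) may be also included in the model". Neither subject nor body side is among its examples, and it commits to nothing.

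Both criteria are decided on interval bounds. Non-inferiority compares "The upper bound 95% confidence interval of the ATE of IP - AC" with 0.5 log10. Superiority compares the lower bound of NC - IP with 1.2 log10.

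For product weight, an exploratory endpoint measured on the same subjects and sides, SAP 7.3.3.3 does specify a random subject effect and a fixed side effect.

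**The concern.** The two sides of one person are unlikely to be independent. Subjects must qualify bilaterally at screening (Protocol 11.3), the test areas are chosen to look alike (Protocol 7.0 and 13.6), and both sides are treated on one day. The baseline covariate may remove only part of what they share. An ordinary regression ignores the remainder and also assumes one residual variance for saline and antiseptics alike.

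At stake is the width of the intervals that decide success. If they are too wide, a product can miss a target it should meet. If too narrow, it can pass wrongly. The plan also asks for no estimate of the within-subject correlation, which a study meant to inform later designs (SAP 4) should supply.

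**Working it through.** **Inputs from the documents.** Four products, two per subject, 12 subjects per pair (SAP 3.3); two-sided alpha 5% (SAP 7.3).

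**Reproducing the plan's counts.** Six pairs x 12 = 72 subjects; x 2 sides = 144 sites per body region. Each product is in three pairs, so 3 x 12 = 36 sites per arm. Any two products share 12 subjects. These agree with the plan. No power is stated, so there is none to reproduce.

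**Assumptions (not in the documents).** rho is the left/right residual correlation after baseline adjustment, taken as 0.1, 0.3 and 0.5. Arm SDs are equal, or saline differs by a stated factor. One model is fitted per body site and time point.

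**True and reported variance.** For arms i and j with SDs s_i and s_j:

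- True: (s_i² + s_j²)/36 - 2 x 12 x rho x s_i x s_j / 36²
- Reported: 2 x (mean of the four arm variances)/36. No subject has two sites in one arm, so this is the expected residual mean square times (1/36 + 1/36).

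*Equal SDs.* The true variance is (2s²/36)(1 - rho/3), so reported/true SE = 1/sqrt(1 - rho/3). For example, rho 0.3 gives 1/sqrt(0.9) = 1.05.

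*Saline SD half the others.* The pooled variance is (3 x 1 + 0.25)/4 = 0.8125 (others = 1). IP-AC: sqrt(0.8125/(1 - rho/3)). NC-IP: sqrt(1.625/(1.25 - rho/3)).

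*Saline SD 1.5 times the others.* The pooled variance is (3 + 2.25)/4 = 1.3125. NC-IP: sqrt(2.625/(3.25 - rho)).

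| Reported/true SE | rho 0.1 | rho 0.3 | rho 0.5 |
|---|---|---|---|
| Equal SDs, either contrast | 1.02 | 1.05 | 1.10 |
| Saline 0.75, IP-AC | 0.96 | 0.995 | 1.03 |
| Saline 0.5, IP-AC | 0.92 | 0.95 | 0.99 |
| Saline 0.5, NC-IP | 1.16 | 1.19 | 1.22 |
| Saline 1.5, NC-IP | 0.91 | 0.94 | 0.98 |

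At rho 0 with saline SD half, IP-AC is sqrt(0.8125) = 0.90. The narrowness therefore comes from pooling the variance, and positive rho offsets it.

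**Precision forgone.** With equal SDs, a random-subject analysis has contrast information [12/(1 - rho) + 6/(1 + rho)]/s², against 18/s² as reported. At rho 0.5 that is (24 + 4) = 28, and sqrt(28/18) = 1.25. At rho 0.1 and 0.3 the SE ratio is 1.02 and 1.10. For scale only, take SD 1.10 (a value in mock Table 8). The IP-AC half-width is then 1.977 x 1.10 x sqrt(2/36) = 0.51 log10 as planned. Modelled, it is 0.47 (rho 0.3) or 0.41 (rho 0.5), against a margin of 0.5.

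**Single-side subjects.** Evaluability is judged per side (SAP 6.1) and shortfalls are made up: "sufficient additional subjects will be recruited and randomized to meet the minimum number of evaluable test sites/treatment arm". With p paired subjects per product pair, reported/true SE = 1/sqrt(1 - rho x p/36). For p = 10, 8, 6 (6, 12, 18 of 36 sites per arm from single-side subjects) this is 1.04, 1.04 (1.035 before rounding), 1.03 at rho 0.3, and 1.08, 1.06, 1.04 at rho 0.5. Dilution is partial.

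**Simulated false non-inferiority.** True IP-AC difference at the 0.5 margin, 4,000 runs per setting, Monte Carlo error about 0.25 points, nominal 2.5%. Assumed: SD 1.10, baseline SD 0.53, baseline within-subject correlation 0.6, slope 0.5.

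| Analysis | Saline SD half: rho 0.1 / 0.3 / 0.5 | Equal SDs: rho 0.1 / 0.3 / 0.5 |
|---|---|---|
| Planned regression | 3.5 / 3.6 / 2.6% | 2.5 / 2.2 / 1.5% |
| Random subject, common variance | 3.6 / 4.2 / 3.5% | not tabulated |
| Random subject, arm-specific variances | 2.5 / 2.8 / 2.3% | 3.0 / 3.2 / 2.3% |
| Planned regression, clustered SE (CR2, Satterthwaite df) | 2.4 / 2.9 / 2.4% | 2.6 / 2.8 / 2.3% |

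A separate simulation (20,000 runs per case, rho 0 to 0.8) used SD 1.1 in all arms, saline 0.54 with the others 1.1, and saline 1.1 with the others 0.72. Coverage of the nominal 95% interval ran from about 92% to 99%. With saline the more variable arm, false superiority was 3.9% at rho 0 and 2.2% at rho 0.8.

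**The case against.** The strongest reply is that two defects are being joined. Ignoring the pairing, with positive rho and similar variances, only makes the intervals conservative. The too-narrow case comes from pooling the variance, is worst at rho 0, and has no support in the documents: the Table 8 SDs are placeholders that show no saline pattern. The size is also modest, since reported/true SE for IP-AC stays within 0.92 to 1.10 in the tabulated cases with saline no more variable than the others. The 0.51 versus 0.41 comparison shows lost efficiency, not invalidity. The study is an unpowered Phase II, and Protocol 7.1 accepts intervals that miss the targets. The SAP attributes the regression to an FDA letter, and clustered SEs alone would restore validity.

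Much of this stands. The two mechanisms are distinct, positive rho always pushes towards wider intervals, and the size is moderate. It does not remove the point. Both mechanisms come from the same unstructured residual, and the plan has no information to say which dominates. If saline is the more variable arm, the superiority interval is the one at risk. The Phase II setting limits the consequence but does not make the intervals valid. The FDA letter was not available here, so nothing rests on it; the clustered-SE option keeps the regression intact.

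**Conclusion.** The point holds and should be fixed. The primary model omits a dependence that the design creates and that the same SAP models for a lesser endpoint. With similar arm variances and rho 0.1 to 0.5, reported SEs are 2% to 10% too large. The cost is precision, not a false claim. With unequal variances, one of the two decision intervals can be somewhat too narrow: SE understated by up to about 9% in the cases tabulated, with simulated one-sided error up to 3.6% for non-inferiority over the same rho range. Point estimates are not biased by the omission when arm variances are similar. All sizes rest on assumed rho and arm SDs. The structural fact, that no subject term is planned, does not.

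**What to change.** In SAP 7.3.1, and correspondingly in Protocol 7.1 and 15.1:

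- State that a separate model is fitted for each body site and time point.
- Add a random subject effect and a fixed side effect, as in SAP 7.3.3.3, to treatment, baseline and the planned interaction step. Allow arm-specific residual variances; a common-variance random-subject model alone does not cure the narrow case.
- Take the IP-AC and NC-IP contrasts and 95% intervals from this model, and name the degrees-of-freedom method.
- Keep subjects with one evaluable side in the analysis.
- Report the estimated within-subject correlation and the residual SD per arm.
- If the plain regression must stay, or the mixed model does not converge, keep the regression estimate and use subject-clustered small-sample SEs (for example CR2 with Satterthwaite degrees of freedom). This is sufficient for validity; the mixed model adds precision.

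Editorial: in Tables 5 and 6 the N Pairs entry of 36 equals the sites per arm, while 12 subjects receive both products of a comparison. Relabel the column and add that number.

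Cost: wording in both documents and a few lines of R, with no new data or subjects. The downside is slightly more complex modelling and, for the mixed model, a more model-dependent point estimate.
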